4.2.3 Safety population

The safety population is the population with at least one LAAC device implanted, and is analysed according to the LAAC device actually implanted.

4.3 Estimands

The primary outcome which is the composite of LAA patency at 45 day evaluated with CCTA; or the crossover from one device to the other device based on morphological/anatomical considerations during device implantation, will be reported as the number of occurrences and the proportion of these occurrences given the number of patients.

CTU Bern	Swiss APERO SAP	Version: 2.0	
	Template: CS_STA_TEM-11	Valid from: 17.08.2021	

CTU Bern	Swiss APERO SAP	Version: 2.0	
	Template: CS_STA_TEM-11	Valid from: 17.08.2021	

5. Trial Population

5.1 Screening data

Screening will be performed up to 90 days prior LAAC. Potential patients will be informed about the study and asked for participation. Subjects are considered provisionally enrolled with the signature on the written informed consent form (screening phase). Formal inclusion into the study will occur after baseline eligibility is confirmed and only once randomization takes place as close as possible to but always before LAAC. A copy of the informed consent form with the patient's information document will be given to the patient.

The following evaluations will be performed at baseline/enrolment:

- *Demographics;*
- *Relevant medical history that includes: general medical, cardiovascular, neurologic and renal history; cardiovascular risk factors (e.g. dyslipidaemia, hypertension, diabetes mellitus, tobacco use); history of peripheral vascular disease, stroke, transient ischemic attack; documentation of current cardiovascular and diabetic medications; Stroke and bleeding risk evaluation with CHADS2, CHA2DS2VASc, HAS-BLEED and ABC score;*
- *Evaluation of In-/Exclusion criteria;*
- *12-lead ECG;*
- *Routine laboratory tests within 48 hours prior to the index procedure as defined in 9.1.7;*
- *CCTA according to current standard of care;*
- *TEE if clinically indicated.*

5.2 Eligibility

Participants fulfilling all the following inclusion criteria are eligible for the study:

- *Written informed consent*
- *Male or female subject aged 18 years or more with no upper age limit and willing to comply with the protocol*
- *Indication to a LAA closure as indicated in study population (HAS BLEED ≥ 3 or High bleeding risk as defined by Munich consensus document and CHA2DS2-VASc ≥ 2).*

The presence of anyone of the following exclusion criteria will lead to exclusion of the participant:

- *New York Heart Association class IV congestive heart failure*
- *ASD or atrial septal repair or closure device*
- *Single occurrence of AF*

CTU Bern	Swiss APERO SAP	Version: 2.0	
	Template: CS_STA_TEM-11	Valid from: 17.08.2021	

- *Cardioversion or ablation procedure planned within 30 days*
- *Implanted mechanical valve prosthesis*
- *Heart transplantation*
- *Enrolled in another IDE or IND investigation of a cardiovascular device or an investigational drug*
- *Female of childbearing potential (age < 50 years and last menstruation within the last 12 months), who did not undergo tubal ligation, ovariectomy or hysterectomy.*
- *Active infection of any kind*
- *Severe chronic kidney insufficiency (CrCl < 30 ml/min)*
- *Terminal illness with life expectancy < 1 year*
- *Echocardiographic exclusion criteria*
- *LVEF < 20%*
- *Intracardiac thrombus or dense spontaneous echo contrast as visualized by TEE within 2 days before implant*
- *Significant mitral valve stenosis (ie, MV < 1.5 cm²)*
- *Complex aortic atheroma with mobile plaque of the descending aorta and/or aortic arch*
- *Cardiac tumor.*

5.3 Recruitment

Patients will be screened previous the admission index. After complete screening pre-evaluation resulting in eligibility for LAAC, patients will be adequate informed and those accepting to participate will sign the informed consent form and will be enrolled in the study by dedicated staff previously identified at each center.

Study participants will not receive any payment or compensation for participation in the study.

CTU Bern	Swiss APERO SAP	Version: 2.0	
	Template: CS_STA_TEM-11	Valid from: 17.08.2021	

5.4 Baseline patient characteristics

A Table of baseline clinical and risk factors will be produced, no comparison randomized to Amulet vs randomized to Watchman will be made.

Table 1. Baseline Clinical Characteristics

	Watchman/FLX N = xx	Amulet N = xx
Demographics		
Age — years mean(SD)	mean +- sd	mean +- sd
Male gender — no. (%)	count (%)	count (%)
Body mass index — kg/m ² mean(SD)	mean +- sd	mean +- sd
Behavioural risk factors		
Smoker — no. (%)	count (%)	count (%)
Alcohol abuse — no. (%)	count (%)	count (%)
Medical history		
Arterial hypertension — no. (%)	count (%)	count (%)
Dyslipidemia — no. (%)	count (%)	count (%)
Family history of CAD — no. (%)	count (%)	count (%)
Diabetes mellitus — no. (%)	count (%)	count (%)
Chronic renal failure — no. (%)	count (%)	count (%)
Uncontrolled hypertension — no. (%)	count (%)	count (%)
Abnormal liver function — no. (%)	count (%)	count (%)
Coronary artery disease — no. (%)	count (%)	count (%)
Documented anaemia — no. (%)	count (%)	count (%)
Long-term oral NSAIDs use — no. (%)	count (%)	count (%)
Long-term steroids use — no. (%)	count (%)	count (%)
Active malignancy — no. (%)	count (%)	count (%)
Prior Cerebrovascular event — no. (%)	count (%)	count (%)
Known carotid artery disease — no. (%)	count (%)	count (%)
History of extracranial systemic embolic events — no. (%)	count (%)	count (%)
History of clinically-overt pulmonary embolism — no. (%)	count (%)	count (%)
Primary reason for an alternative to OAC		
History of Major bleedings	count (%)	count (%)
Wish to avoid triple therapy	count (%)	count (%)
Risk of fall or prior falls	count (%)	count (%)
Concomitant disease increasing bleeding risk	count (%)	count (%)
HASBLED score >=3	count (%)	count (%)
Rejection of OAC	count (%)	count (%)
Embolic event under OAC	count (%)	count (%)
Others	count (%)	count (%)
Prior myocardial infarction — no. (%)	count (%)	count (%)

CTU Bern	Swiss APERO SAP	Version: 2.0	
	Template: CS_STA_TEM-11	Valid from: 17.08.2021	

Valvular heart disease — no. (%)	count (%)	count (%)
History of heart failure — no. (%)	count (%)	count (%)
Decompensated heart failure at randomisation — no. (%)	count (%)	count (%)
EHRA III — no. (%)	count (%)	count (%)
Ejection fraction — mean (SD)	mean +- sd	mean +- sd
Pacemaker or ICD — no. (%)	count (%)	count (%)
CHA2DS2VASC Score — mean(SD)	mean +- sd	mean +- sd
— no. (%)		
0	count (%)	count (%)
1	count (%)	count (%)
2	count (%)	count (%)
3	count (%)	count (%)
4	count (%)	count (%)
5	count (%)	count (%)
6	count (%)	count (%)
7	count (%)	count (%)
8	count (%)	count (%)
HASBLED Score — mean(SD)	mean +- sd	mean +- sd
— no. (%)		
0	count (%)	count (%)
1	count (%)	count (%)
2	count (%)	count (%)
3	count (%)	count (%)
4	count (%)	count (%)
5	count (%)	count (%)
6	count (%)	count (%)
Atrial fibrillation or flutter — no. (%)		
paroxysmal — no. (%)	count (%)	count (%)
persistent or chronic — no. (%)	count (%)	count (%)
undetermined — no. (%)	count (%)	count (%)
atrial flutter — no. (%)	count (%)	count (%)
History of relevant bleeding — no. (%)	count (%)	count (%)
Intracranial bleeding — no. (%)	count (%)	count (%)
Gastrointestinal bleeding — no. (%)	count (%)	count (%)
Urinary — no. (%)	count (%)	count (%)
Epistaxis — no. (%)	count (%)	count (%)
Other bleeding — no. (%)	count (%)	count (%)
unknown — no. (%)	count (%)	count (%)

Data expressed as n (%) or means±standard deviations.

MI: myocardial infarction; LAA: left-atrial appendage; EHRA: European Heart Rhythm score.

CTU Bern	Swiss APERO SAP	Version: 2.0	
	Template: CS_STA_TEM-11	Valid from: 17.08.2021	

5.5 LAAC procedural characteristics

A Table of LAAC details will be produced comparing randomized to Amulet vs randomized to Watchman. In case none or very few second, third or fourth devices are used or implanted, this table will be simplified accordingly.

Table 2. LAAC Procedural Characteristics

	Watchman/FLX N = xx	Amulet N = xx	p-value
Starting cardiac rhythm— no. (%)			x.xxx
Sinus	count (%)	count (%)	x.xxx
Atrial fibrillation or flutter	count (%)	count (%)	x.xxx
Other (e.g.pacemaker)	count (%)	count (%)	x.xxx
General anaesthesia — no. (%)	count (%)	count (%)	x.xxx
Left atrium reached by — no. (%)			x.xxx
atrial septum	count (%)	count (%)	x.xxx
fossa ovalis	count (%)	count (%)	x.xxx
PFO or ASD	count (%)	count (%)	x.xxx
Nr of transeptal punctures — no. (%)			x.xxx
zero	count (%)	count (%)	x.xxx
one	count (%)	count (%)	x.xxx
two or more	count (%)	count (%)	x.xxx
Distance between puncture and mitral plane — mm (SD)	mean +- sd	mean +- sd	x.xxx
Mean left atrial pressure before implantation — mmHg	mean +- sd	mean +- sd	x.xxx
Intracardiac echocardiography — no. (%)	count (%)	count (%)	x.xxx
Procedure time — minutes	mean +- sd	mean +- sd	x.xxx
Fluoroscopy time — minutes	mean +- sd	mean +- sd	x.xxx
Contrast medium — ml med(IQR)	mean +- sd	mean +- sd	x.xxx
Contrast medium/body mass — ml/kg	mean +- sd	mean +- sd	x.xxx
X-ray dose — cGy.cm ² med(IQR)	median (IQR)	median (IQR)	x.xxx
Concomitant procedure* — no. (%)	count (%)	count (%)	x.xxx
Final device			
LAAC device — no. (%)			x.xxx
Amulet	count (%)	count (%)	x.xxx
Watchman	count (%)	count (%)	x.xxx
Watchman FLX	count (%)	count (%)	x.xxx
Implanted device size — mm (SD)	mean +- sd	mean +- sd	x.xxx
Procedure aborted	count (%)	count (%)	x.xxx
All LAAC devices			
Total Nr of implantation attempts — no. (%)			x.xxx
1	count (%)	count (%)	x.xxx
2	count (%)	count (%)	x.xxx

CTU Bern	Swiss APERO SAP	Version: 2.0	
	Template: CS_STA_TEM-11	Valid from: 17.08.2021	

3	count (%)	count (%)	x.xxx
4 or more	count (%)	count (%)	x.xxx
Total Nr of partial recaptures — no. (%)			x.xxx
0	count (%)	count (%)	x.xxx
1	count (%)	count (%)	x.xxx
2	count (%)	count (%)	x.xxx
3	count (%)	count (%)	x.xxx
4 or more	count (%)	count (%)	x.xxx
Total Nr of complete recaptures — no. (%)			x.xxx
0	count (%)	count (%)	x.xxx
1	count (%)	count (%)	x.xxx
2	count (%)	count (%)	x.xxx
3	count (%)	count (%)	x.xxx
4 or more	count (%)	count (%)	x.xxx
Total nr of LAAC devices implanted			x.xxx
none	count (%)	count (%)	x.xxx
one	count (%)	count (%)	x.xxx
two	count (%)	count (%)	x.xxx
Total nr of LAAC devices used			x.xxx
1	count (%)	count (%)	x.xxx
2	count (%)	count (%)	x.xxx
3	count (%)	count (%)	x.xxx
End of procedure cardiac rhyth no. (%)			x.xxx
Sinus	count (%)	count (%)	x.xxx
Atrial fibrillation or flutter	count (%)	count (%)	x.xxx
Pacemaker (incl temporary pacer)	count (%)	count (%)	x.xxx
Post-procedure peri-LAAC device leaks PDL — no. (%)			
Any PDL detected by TEE or Angiography?	count (%)	count (%)	x.xxx
detected by TEE only	count (%)	count (%)	x.xxx
detected by Angiography only	count (%)	count (%)	x.xxx
detected by TEE and Angiography	count (%)	count (%)	x.xxx
Periprocedural complications — no . (%)			
Death	count (%)	count (%)	x.xxx
Stroke or TIA	count (%)	count (%)	x.xxx
Bleeding	count (%)	count (%)	x.xxx
BARC 1	count (%)	count (%)	x.xxx
BARC 2	count (%)	count (%)	x.xxx
BARC 3abc	count (%)	count (%)	x.xxx
BARC 4	count (%)	count (%)	x.xxx
BARC 5ab	count (%)	count (%)	x.xxx
BARC 3-5	count (%)	count (%)	x.xxx
Peripheral or pulmonary embolization	count (%)	count (%)	x.xxx
Pericardial effusion (new onset)	count (%)	count (%)	x.xxx
Pericardial effusion clinically relevant	count (%)	count (%)	x.xxx

CTU Bern	Swiss APERO SAP	Version: 2.0	
	Template: CS_STA_TEM-11	Valid from: 17.08.2021	

Vascular access site complication	count (%)	count (%)	x.xxx
Device embolization	count (%)	count (%)	x.xxx
Acute kidney injury	count (%)	count (%)	x.xxx
Electrical or mechanical resuscitation	count (%)	count (%)	x.xxx

Data expressed as n (%), p-value from Fisher's tests) or means±standard deviations (p-value from unpaired t-tests) or median[IQR] (p-value from Mann-Whitney U-test).

LAAC: left-atrial appendage closure; PFO: patent foramen ovale; ASD: atrial septal defect; ICU: intensive care unit; TIA: transient ischemic attack; TEE: transoesophageal echocardiography.

* Coronary angiography included

CTU Bern	Swiss APERO SAP	Version: 2.0	
	Template: CS_STA_TEM-11	Valid from: 17.08.2021	

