4.1 Confidence intervals and *P* values

Primary and secondary end points will be analysed on an intention-to-treat basis. Additional analyses will be also carried out in the per-protocol and as-treated populations. Categorical outcome measures will be compared using a χ^2 test or Fisher exact test as required. Continuous variables will be compared using a 2-sided unpaired t test or a Mann-Whitney test, as appropriate. Estimation of the cumulative incidence of safety and efficacy end-points will be performed using the Kaplan-Meier method in case of time-to-event endpoints, and event rates will be compared by the log rank test. The estimated relative risk (RR) is the ratio of the risk probabilities, and a confidence interval will be constructed based on a logarithmic transformation.

The primary endpoint LAA patency or adjudicated cross-over including failed cross-over to other device at 45 days will be analyzed using risk ratios and risk differences.

All statistical tests will be performed using a 5% significance level.

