6.1.2 Secondary outcome

Secondary outcomes are:

- *LAA patency (arterial and/or venous phase) at 45 day CCTA and 13-month CCTA in the per protocol and as treated populations*
- *All cause of death, stroke, systemic or pulmonary embolism and spontaneous MI*
- *Cardiovascular death*
- *Ischemic stroke*
- *Hemorrhagic stroke*
- *Bleeding events according to the BARC classification at each follow-up.*
- *Procedure-related complications*
- *Rate of patients on (N)OAC at 45 days and 6 months*
- *Device related thrombosis at 45 day TEE/CCTA and 13-month CCTA in the per protocol and as treated populations*
- *Feasibility outcome (number of device implantation attempts, total time procedure, x-ray dose and total contrast dose used in the procedure)*
- *LAA patency at 45 day TEE in the per protocol and as treated populations*

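### Cheap improvement: SAP Table 2 (section 5.5) gives the number of implantation attempts, an ordered count and secondary outcome, a Fisher test that ignores the ordering and loses power against a consistent shift

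*Combined protocol and SAP*

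**What the plan says.** SAP 6.1.2 lists among the secondary outcomes: "Feasibility outcome (number of device implantation attempts, total time procedure, x-ray dose and total contrast dose used in the procedure". Protocol 17.14 defines an attempt and has partial and complete recaptures recorded under it. SAP 6.1.4 and protocol 5.6 add the number of devices of the same type used.

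Table 2 in SAP 5.5 shows four ordered counts as categories with a p-value column:

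- "Total Nr of implantation attempts — no": 1, 2, 3, 4 or more.
- "Total Nr of partial recaptures — no", and the matching row for complete recaptures: 0, 1, 2, 3, 4 or more.
- "Total nr of LAAC devices used": 1, 2, 3.

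A further row gives devices implanted as none, one or two. The footnote sets the tests: "Data expressed as n (%), p-value from Fisher's tests) or means±standard deviations (p-value from unpaired t-tests) or median[IQR] (p-value from Mann-Whitney U-test".

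The general rules in SAP 4.1 are: "Categorical outcome measures will be compared using a χ^2 test or Fisher exact test as required", and "Continuous variables will be compared using a 2-sided unpaired t test or a Mann-Whitney test, as appropriate". Neither rule mentions counts, and no trend or ordinal test is named for these rows.

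**The concern.** The feasibility question has a direction: does one device take more attempts than the other? An unordered test on a 2×4 table treats 4 or more as no further from 1 than 2 is. It spreads its sensitivity over three degrees of freedom, where a consistent shift needs only one. A real difference in ease of implantation, which SAP 2.4 puts in the study hypotheses, could then be missed when an available test would have had a better chance of showing it. What is at stake is the efficiency of a secondary comparison, not the validity of a result.

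**Working it through.** **Inputs from the documents.** 100 patients per arm (protocol synopsis), 1:1 allocation (SAP 2.2), 5% significance level (SAP 4.1, taken as two-sided), and the category layouts above.

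**The plan's own figure.** Only the primary endpoint is powered: 50% vs 30%, more than 80% power (SAP 2.3). With a pooled rate of 0.40:

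Φ[(0.20 − 1.96·√(2·0.40·0.60/100)) / √(0.25/100 + 0.21/100)] = Φ[(0.20 − 0.1358)/0.0678] = Φ(0.947) = 82.8%.

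That reproduces. No power is stated for any feasibility outcome.

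**Inputs that must be assumed.** The documents give no expected distribution of attempts, recaptures or devices used, and no effect size. I varied the base distribution and applied a proportional-odds shift. With F_j the cumulative share up to category j in one arm, the other arm has G_j = OR·o_j/(1 + OR·o_j), where o_j = F_j/(1 − F_j).

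Example, base 60/22/11/7 and OR 2: the odds 1.5, 4.556 and 13.286 double to 3.0, 9.111 and 26.571. This gives G = 0.750, 0.901, 0.964, so the second arm is 75.0/15.1/6.3/3.6.

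**Tests compared.**

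- Fisher: the exact r×c (Freeman-Halton) test, which sums the probabilities of all tables with the same margins that are no more likely than the one observed. It does not change if columns are reordered.
- Mann-Whitney: normal approximation with tie correction, on the same collapsed categories.

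**Power for attempts (four categories), Fisher vs Mann-Whitney, %.** 4,000 simulated trials per cell; 3,000 in the first row.

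| Base (1/2/3/4+) | OR 1.5 | OR 2 | OR 3 | OR 4 |
|---|---|---|---|---|
| 40/30/18/12 | 20.5 vs 33.2 | 54.5 vs 72.6 | 93.3 vs 97.7 | 99.1 vs 99.9 |
| 50/25/15/10 | 21.6 vs 33.6 | 53.5 vs 70.1 | 90.6 vs 96.6 | 98.4 vs 99.6 |
| 60/22/11/7 | 18.6 vs 30.0 | 47.5 vs 64.3 | 85.3 vs 93.9 | 95.7 vs 98.9 |
| 70/18/8/4 | 16.7 vs 24.7 | 38.4 vs 55.4 | 74.4 vs 88.0 | 89.6 vs 96.4 |
| 80/14/4/2 | 12.7 vs 18.1 | 30.7 vs 42.1 | 59.7 vs 73.6 | 77.2 vs 86.9 |

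The losses at OR 2, top to bottom, are 18.1, 16.6, 16.8, 17.0 and 11.4 points. Over the whole table they run from about 1 point (99.9 − 99.1 = 0.8) to 18.1. A separate simulation with Pearson's chi-square in place of the exact test gave 56% vs 74% at OR 2 on a 55/25/12/8 base, and a largest loss of about 19. I therefore quote 1 to 19 overall and 11 to 19 at OR 2.

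**Devices used (three categories).** Bases 85/12/3 and 75/20/5, OR 1.5 to 4: the loss runs from 3.8 points (12.6 vs 16.4) to 10.9 (38.1 vs 49.0).

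**Recaptures (five categories).** Bases 60/20/10/6/4 and 75/14/6/3/2, OR 1.5 to 2.5: about 10 to 20 points. Only 600 trials were run per scenario, so one power near 50% has a standard error of √(0.25/600) = 2.0 points.

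**Size.** With no difference between arms, rejection rates were 4.4% to 5.3% for the two tests, in the four- and three-category scenarios run with 4,000 trials.

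**Where the ranking reverses.** Against 60/22/11/7, the alternative 60/33/5/2 gives Fisher 61% and Mann-Whitney 10%; the alternative 70/8/12/10 gives 67% and 16%.

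**The case against.** - **The alternatives favour Mann-Whitney.** Proportional-odds shifts are the setting in which a rank test does well, and the two reversed cases show the price. In 70/8/12/10 the arms cross, and that is not the feasibility question. In 60/33/5/2 the share done in one attempt is equal and the difference lies only among the rest. It is not a steady shift across the scale, though a reader could still find it relevant. This stands as a small downside, and it is a reason to keep the category percentages on display.
- **A fixed loss.** A reader might take the 17 or so points seen in several cells at OR 2 as a property of the plan. The documents do not support that. They state no distribution or effect, the loss falls to about 1 point for very large shifts, and the figure does not carry over to devices used.
- **An invalid test or inflated error.** A reader might infer this, especially since the shell prints a p-value on each category line as well as on the variable. The overall Fisher test holds its size. The per-line entries may be template filler: the same placeholder runs down nearly every row, and the contrast-volume row is labelled median (IQR) but filled as mean and SD. They are worth tidying but do not show a planned multiple-testing fault.
- **Device rows may collapse.** SAP 5.5 says the table will be simplified if very few further devices are used. With two levels left there is no ordering to lose. That stands for devices used, but not for attempts.
- **Scope.** Recaptures are not listed as outcomes in SAP 6.1.2 or 6.1.4. The attempts row sits under all devices, so it can include attempts with a crossover device, whereas SAP 6.1.4 speaks of attempts with a single device. Changing the test does not settle which count is meant.
- **SAP 4.1 might already allow it.** Mann-Whitney is permitted there for continuous variables, but counts are not mentioned and the Table 2 footnote points to Fisher.

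**Conclusion.** The point holds as a cheap improvement. As written, the SAP compares an ordered count that belongs to a secondary outcome with a valid test that ignores the ordering. For a consistent shift between devices at 100 per arm, the cost is roughly 1 to 19 percentage points of power for attempts, about 11 to 19 at OR 2, and about 4 to 11 for devices used. These ranges rest on assumed category distributions and proportional-odds shifts, and they should always be quoted with those assumptions. The direction is firm for shifts of that kind and reverses for some differences that do not run steadily across the categories. The binary primary endpoint is untouched.

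**What to change.** Amend the footnote to Table 2 in SAP 5.5:

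1. Test "Total Nr of implantation attempts — no" and "Total nr of LAAC devices used" as uncollapsed counts with the Mann-Whitney test already named in SAP 4.1. Do the same for partial and complete recaptures, presented as descriptive companions to attempts and not as separate outcomes.
2. Print one p-value per variable, and keep the category percentages as description only.
3. Keep Fisher's test for devices implanted (none, one, two). None means that no device was placed, so it is not the favourable end of an ordered scale, and a rank test could let an excess of none and an excess of two cancel.

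The cost is a footnote and a line of code, with no new data and no design change. SAP 4.2.2 already lists the attempts with the first device as a numeric variable. The price is lower sensitivity to differences that are not a consistent shift, which the displayed percentages would still show. The change should be dated before anyone sees these rows by arm.

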5.6 Medication

A Table of medications at each visit will be produced, comparing randomized to Amulet vs randomized to Watchman.

Table 3. Medication use

	Watchman/FLX N = xx	Amulet N = xx	p-value
within 7 days before LAAC — no. (%)			
Aspirin	count (%)	count (%)	
Clopidogrel	count (%)	count (%)	
Prasugrel	count (%)	count (%)	
Ticagrelor	count (%)	count (%)	
Vitamin K-antagonist	count (%)	count (%)	
NOAC	count (%)	count (%)	
Dabigatran	count (%)	count (%)	
Rivaroxaban	count (%)	count (%)	
Apixaban	count (%)	count (%)	
Edoxaban	count (%)	count (%)	
Others	count (%)	count (%)	
Low-molecular weight heparin	count (%)	count (%)	
Therapy			
None	count (%)	count (%)	
SAPT *	count (%)	count (%)	
DAPT **	count (%)	count (%)	
OAC ***	count (%)	count (%)	
SAPT+OAC	count (%)	count (%)	
Triple therapy ***	count (%)	count (%)	
During/after LAAC procedure § — no. (%)			
Aspirin			x.XXX
maintenance dose	count (%)	count (%)	x.XXX
loading dose	count (%)	count (%)	x.XXX
No	count (%)	count (%)	x.XXX
Clopidogrel			x.XXX
maintenance dose	count (%)	count (%)	x.XXX
loading dose 300mg	count (%)	count (%)	x.XXX
loading dose 600mg	count (%)	count (%)	x.XXX
No	count (%)	count (%)	x.XXX
Prasugrel			x.XXX

CTU Bern	Swiss APERO SAP	Version: 2.0	
	Template: CS_STA_TEM-11	Valid from: 17.08.2021	

maintenance dose	count (%)	count (%)	x.xxx
loading dose 60mg	count (%)	count (%)	x.xxx
No	count (%)	count (%)	x.xxx
Ticagrelor			x.xxx
maintenance dose	count (%)	count (%)	x.xxx
loading dose 180mg	count (%)	count (%)	x.xxx
No	count (%)	count (%)	x.xxx
Vitamin K-antagonist	count (%)	count (%)	x.xxx
NOAC	count (%)	count (%)	x.xxx
NOAC Type			x.xxx
Dabigatran	count (%)	count (%)	x.xxx
Rivaroxaban	count (%)	count (%)	x.xxx
Apixaban	count (%)	count (%)	x.xxx
Edoxaban	count (%)	count (%)	x.xxx
Others	count (%)	count (%)	x.xxx
Low-molecular weight heparin	count (%)	count (%)	x.xxx
Discharge — no. (%) ¶	n=xx	n=xx	
Aspirin	count (%)	count (%)	x.xxx
Clopidogrel	count (%)	count (%)	x.xxx
Prasugrel	count (%)	count (%)	x.xxx
Ticagrelor	count (%)	count (%)	x.xxx
Vitamin K-antagonist	count (%)	count (%)	x.xxx
NOAC	count (%)	count (%)	x.xxx
NOAC Type			x.xxx
Dabigatran	count (%)	count (%)	x.xxx
Rivaroxaban	count (%)	count (%)	x.xxx
Apixaban	count (%)	count (%)	x.xxx
Edoxaban	count (%)	count (%)	x.xxx
Others	count (%)	count (%)	x.xxx
Low-molecular weight heparin	count (%)	count (%)	x.xxx
Therapy			x.xxx
None	count (%)	count (%)	x.xxx
SAPT *	count (%)	count (%)	x.xxx
DAPT **	count (%)	count (%)	x.xxx
OAC ***	count (%)	count (%)	x.xxx
SAPT+OAC	count (%)	count (%)	x.xxx
Triple therapy ***	count (%)	count (%)	x.xxx
Follow-up 45 days — no. (%) ¶	n=xx	n=xx	
Aspirin	count (%)	count (%)	x.xxx

CTU Bern	Swiss APERO SAP	Version: 2.0	
	Template: CS_STA_TEM-11	Valid from: 17.08.2021	

Clopidogrel	count (%)	count (%)	x.xxx
Prasugrel	count (%)	count (%)	x.xxx
Ticagrelor	count (%)	count (%)	x.xxx
Vitamin K-antagonist	count (%)	count (%)	x.xxx
NOAC	count (%)	count (%)	x.xxx
NOAC Type	count (%)	count (%)	x.xxx
Dabigatran	count (%)	count (%)	x.xxx
Rivaroxaban	count (%)	count (%)	x.xxx
Apixaban	count (%)	count (%)	x.xxx
Edoxaban	count (%)	count (%)	x.xxx
Others	count (%)	count (%)	x.xxx
Low-molecular weight heparin	count (%)	count (%)	x.xxx
Therapy	count (%)	count (%)	x.xxx
None	count (%)	count (%)	x.xxx
SAPT *	count (%)	count (%)	x.xxx
DAPT **	count (%)	count (%)	x.xxx
OAC ***	count (%)	count (%)	x.xxx
SAPT+OAC	count (%)	count (%)	x.xxx
Triple therapy ***	count (%)	count (%)	x.xxx

Data expressed as n (%) and p-values are from Fisher's tests.

* SAPT (Only Aspirin, Only Clopidogrel, Only Prasugrel, Only Ticagrelor)

** DAPT (Aspirin+Clopidogrel, Aspirin+Prasugrel, Aspirin+Ticagrelor)

*** OAC (NOAC, Vitamin K-Antagonist, Low molecular weight heparin)

**** Triple therapy (any combination between DAPT groups AND OAC groups)

§ within 6 hours of the device implantation

¥ xx patients died before discharge

¶ xx patients did not perform 45 day followup

CTU Bern	Swiss APERO SAP	Version: 2.0	
	Template: CS_STA_TEM-11	Valid from: 17.08.2021	

